This will be a randomized, double blind, placebo controlled trial of 7 days of oral prednisone in CF patients receiving IV antibiotic treatment for a pulmonary exacerbation at the Hospital for Sick Children, and multiple sub-sites, both adult and paediatric populations across Canada..

Eligible patients will be randomized over a recruitment period of 3 years. Each patient can only be randomized in the study once.

Study inclusion criteria

1. Diagnosis of CF by newborn screening or at least one clinical feature of CF, AND either (a) or (b) as follows:
 - a) A documented sweat chloride ≥ 60 mEq/L by quantitative pilocarpine iontophoresis
 - b) A genotype with two identifiable CF-causing mutations
2. Age > 6 years old.
3. Acute pulmonary exacerbation treated with IV antibiotics as previously defined
 - 10% relative drop in FEV₁ from baseline at the time of exacerbation
4. Informed consent by patient or parent/legal guardian
5. Ability to reproducibly perform pulmonary function testing
6. Ability to comply with medication use including the ability to take capsules, study visits and study procedures as judged by the site investigator

Study exclusion criteria

1. A respiratory tract culture positive for *Burkholderia cenocepacia* in the 12 months prior to enrollment
2. A respiratory tract culture positive for *Mycobacterium abscessus* in the 12 months prior to enrollment
3. Treatment with IV or oral corticosteroids within 2 weeks of enrollment or from Day 0-Day 7 of the pulmonary exacerbation
4. Active allergic bronchopulmonary aspergillosis (ABPA) at the time of enrollment as determined by treating physician
5. Asthma related exacerbation at enrollment as defined by the treating physician based on clinically compatible symptoms (eg. wheeze)
6. History of avascular necrosis or pathologic bone fracture
7. Uncontrolled hypertension with end organ damage
8. Active gastrointestinal bleeding
9. Status post lung or other organ transplantation
10. Pregnancy
11. Lactose intolerance (contained in placebo)
12. On Lumacaftor-Ivacaftor (Orkambi) at the time of exacerbation
13. Investigational drug use within 30 days prior to enrollment visit
14. Physical findings that would compromise the safety of the subject or the quality of the study data as determined by site investigator

D. Study protocol

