Randomization (1:1) will be done through central allocation of a block-randomization schedule prepared through a computer-generated random listing. Randomization will be done by the study data analyst at the Hospital for Sick Children. The analyst will be the only member of the investigative team aware of the randomization assignment and will not be directly doing the statistical analysis. He/she will not be involved in the care of the study patients or the measurement of outcomes in the study. No other research staff nor patients nor physicians will be aware of the randomization assignment. The pharmacist at each study site will call the analyst for randomization.

Once the patient is randomized, the analyst will inform the research pharmacy at each study site and they will distribute either prednisone or placebo (lactose, packaged in #0 capsules of identical appearance) to the hospital ward or the CF clinic according to dosing Table 1. Physicians and patients will be blinded to the treatment, and placebo will be produced to look identical to the treatment drug. The microbiology lab and pulmonary function lab will also be blinded to the treatment allocation. Compliance will be measured by nurses for hospitalized patients and by asking patients to return any unused medication for patients receiving homecare IV antibiotics.

Safety monitoring

Patients who are most at risk of developing side effects secondary to corticosteroid use will be excluded based on the above exclusion criteria. Subjects will be monitored with measurements of urine glucose on day 7, day 10 (\pm 2 days) and on day 14 of antibiotic treatment while on prednisone (or placebo). If the urine glucose is $> 2+$, a serum glucose measurement will be performed. All the information will be provided to the treating physicians; they can decide at any time to withdraw their patient and request unblinding of the treatment allocation. The study will be monitored by a Data Safety Monitoring Board (DSMB) (Appendix 1.2-Data Safety Monitoring Plan).

E. Study outcomes:

Primary outcome:

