conferences (North American CF conference, European CF conference) and talking to patient communities at CF Chapter meetings. We will also develop a plain language summary for dissemination at conferences, on the CF Canada website and through CF newsletters. Through our strong collaboration with CF centers across Canada and with the assistance of CF Canada, we will disseminate results through teleconferences and other regular encounters with Canadian CF clinic directors.

K. Deliverables and Future Directions:

If the study subjects in this trial treated with oral prednisone have significantly better recovery of FEV₁ after antibiotic treatment for a pulmonary exacerbation compared to controls, without suffering more adverse effects, we will have identified an effective, available and inexpensive treatment option that can be readily instituted into clinical practice. However, if the observed differences are still clinically meaningful but not statistically significant, we will determine the required sample size and if feasible, expand the trial into other Canadian or US CF sites. We have also applied to the US CF Foundation for funding of this study and to gauge their interest in participation. In addition, this large, multi-center interventional study will serve as a platform for sub-studies of pulmonary exacerbations. Within our consortium of Canadian CF researchers, we have formed a sub-group of investigators to examine biomarkers of exacerbations using stored serum and sputum samples collected as part of this trial. We therefore expect this project to significantly expand our knowledge of CF pulmonary exacerbations. Our ultimate goal is to improve lung function recovery following these events in order to extend the survival of individuals with CF.

L. References

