Appendix 1.2

Data Safety Monitoring Plan

Although subjects will be randomized to either oral prednisone or placebo, no investigational drug will be tested in this trial. Upon funding of the study, the study will be submitted to the Research Ethics Board (REB) at the Hospital for Sick Children and all other study sub-sites). REB comments and amendments will be distributed to all sites in order to ensure that the approved study protocol is identical at all sites.

Assessment of Risk

The assessment of risk is deemed to be **moderate** in this trial due to the known side effects of prednisone (eg. hyperglycemia, hypertension, gastrointestinal bleeding). Given that we will be treating subjects with a short course of oral prednisone (7 days), we do not expect to observe the long-term side effects noted with more prolonged steroid use (eg. growth retardation, osteopenia/avascular necrosis). Although certain subjects will receive placebo, they will still be receiving antibiotic treatment for the pulmonary exacerbation which is standard of care.

Anticipated Adverse Events and Grading Scale

In the previous study by Dovey et al. 12 CF subjects received oral prednisone (2 mg/kg/day x 5 days) and 12 subjects received placebo during treatment for a pulmonary exacerbation (13).

The most common adverse events were glucosuria, hyperglycemia and hypertension.

Hypertension was reported for 2 subjects in each arm, with one prednisone treated subject withdrawn on day 2 due to this. Glucosuria was reported among 6 subjects in the prednisone arm and 1 in the placebo arm ($p=0.03$); 2 of the subjects in the prednisone arm with glucosuria also had hyperglycemia (1 of these was withdrawn due to this). Additional adverse events included headache, restlessness, heartburn, nausea/epigastric pain, swelling, increased thirst and increased urination. There were no serious events in either treatment arm.

We therefore anticipate the most common adverse events to be hyperglycemia (random serum glucose > 200 mg/dL or 13 mmol/L)(55), glucosuria ($> 1+$ urine glucose) and hypertension (defined as the 99th percentile of blood pressure measurement according to gender, age and

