height using the NIH guidelines(56)) and will monitor for these adverse events (see below-Safety Monitoring Plan). In addition, all untoward medical occurrences, whether or not deemed causally related to study participation, will be recorded and site investigators will be asked to assess both severity and whether or not the adverse event was related to study participation. We will use the following grading scale to assess adverse events:

Adverse Event Category	Description
Mild	transient event, no treatment change, e.g. glucosuria
Moderate	treatment discontinued e.g. severe/sustained hypertension or hyperglycemia
Severe	severe: death, unexpected hospitalization

Given that subjects will be randomized at the time of hospitalization for a pulmonary exacerbation, we will monitor the time to subsequent exacerbation. If we observe a shorter time to subsequent exacerbation in one of the treatment arms, this will be reported to the DSMB.

Reporting of AEs

All adverse events will be recorded by the research coordinator and reported to the study site investigator as well as the PI ([name]), who will oversee close and continuous monitoring for safety concerns throughout the trial. All serious adverse events will be reported to Health Canada, based on the Health Canada Guidance: Adverse Drug Reactions (ADRs) Reporting Criteria. All serious and unexpected adverse events will also be reported to the REB at each study site as well the REB at the Hospital for Sick Children (as study sponsor) within 48 hours of their occurrence. Adverse events will also be reported to the Data Safety Monitoring Board (DSMB) (see below) in the form of regular reports submitted every 6 months. Serious adverse events will be reported to the DSMB within 48 hours.

Safety Monitoring Plan

Hospitalized subjects will be monitored on day 7, day 10 (+/- 2 days) and on day 14 with urine dip glucose measurements while on prednisone (or placebo). If the urine glucose is > 2+, a serum glucose measurement will be performed. All the information will be provided to the treating physicians; they can decide at any time to withdraw their patient and request unblinding of the treatment allocation. To unblind a subject, the research coordinator or physician will call the PI ([name]) at [contact] [name] or page [contact]

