who will then request unblinding from the study data analyst. Additionally, subjects will also have a blood pressure done on day 7, day 10 (+/- 2 days) and on day 14 as part of their vital signs assessment. The research coordinator will also visit the subject daily to record all adverse events.

For patients who receive their treatment at home with home intravenous antibiotic therapy, they will be taught how to test their urine glucose (or parents in the case of children) on day 7, day 10 (+/- 2 days) and on day 14 and told to call the research coordinator with the result and report their adverse events. If the urine glucose is > 2+, they will be asked to come to clinic to have a serum glucose drawn and reported to the research coordinator as well as responsible physician. The home care nurse (or via home ambulatory machine) will also do the blood pressure check on day 7, day 10 (+/- 2 days) and on day 14 and report it to the research coordinator as well as responsible physician. The decision to withdraw a subject based on adverse events of hypertension or hyperglycemia will be made by the treating physician. Once the 7 days of treatment (prednisone or placebo) are completed, the subjects will be instructed to call the research coordinator with serious adverse events such as a re-hospitalization for a pulmonary exacerbation. At the follow up clinic visit, the research coordinator will once again review adverse events with the subject.

Diabetic patients on insulin may have disruption of their glucose control while on prednisone. Therefore, as per standard clinical care, diabetic patients on insulin will do daily blood glucose monitoring and adjust their insulin accordingly as per published guidelines{Committee, 2018 #83}. This will be performed and monitored by the clinical team and treating physicians as per standard of care. Diabetic patients for whom glucose control has become unmanageable will be discontinued from the study as per the treating physician's assessment.

Safety Reviews

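### Glucosuria, hyperglycaemia and hypertension are defined by a threshold alone, with no pre-dose reference, so abnormalities present before dosing count as events; no separate adult hypertension criterion is stated

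*Combined protocol and SAP*

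**What the plan says.** Appendix 1.2 (Anticipated Adverse Events and Grading Scale) gives three definitions. Hyperglycaemia is "random serum glucose > 200 mg/dL or 13 mmol/L". The next two begin "glucosuria ($> 1+$ urine glucose) and hypertension". The hypertension cut-off is "defined as the 99th percentile of blood pressure measurement according to gender, age and"; the sentence then adds height as a third factor and cites NIH guidelines (reference 56) as its source. Reference 56 is listed by title as a table of blood pressure by age and height percentile. Severity is then graded by whether treatment was changed or stopped, and site investigators judge relatedness.

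Table 2 and Appendix 1.2 (Safety Monitoring Plan) schedule a urine dip and a blood pressure on days 7, 10 and 14 for randomised patients. Neither is marked at day 0. Section D (Safety monitoring) describes "measurements of urine glucose on day 7, day 10 (\pm 2 days) and on day 14 of antibiotic treatment while on prednisone (or placebo"). Serum glucose is drawn only if the dip exceeds 2+.

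On who may enter, Section C sets the trial in "multiple sub-sites, both adult and paediatric populations across Canada", with a lower age limit and no upper one. Its exclusion list names hypertension only when it is uncontrolled and has caused end-organ damage, and it does not name diabetes. Section F calls diabetes treated with insulin an exclusion. Section G plans a comparison of diabetic with non-diabetic participants, and Appendix 1.2 says that "diabetic patients on insulin will do daily blood glucose monitoring and adjust their insulin accordingly".

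Section E makes the number of adverse events by arm secondary outcome vi. Section K says that if prednisone patients recover better "without suffering more adverse effects, we will have identified an effective, available and inexpensive treatment option".

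**The concern.** A harm attributable to seven days of study drug is one that appears or worsens after the first dose. The definitions do not ask for that. A participant whose dip already exceeds 1+, or whose blood pressure already exceeds the percentile, meets the definition before taking a capsule. The protocol makes such participants foreseeable, since it plans for diabetics and admits most people with hypertension.

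The natural reference is the day-7 check, but it is not secured. Study drug is dispensed on the same day, no text orders the check before the first dose, and no earlier dip or blood pressure is scheduled. If a site doses first, no protocol-specified pre-dose value exists.

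At stake is the comparison in outcome vi. Events unrelated to treatment that are counted in both arms pull it towards no difference, and the absence of excess harm is part of the case that Section K would make for adopting prednisone. Separately, an adult site reads a hypertension rule stated only as an age-and-height percentile and finds no other.

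**Working it through.** **Text check.** The places that deal with adverse events are Section D (Safety monitoring), Section E (outcome vi), Table 2 and Appendix 1.2. None compares a day-10 or day-14 value with day 7, none uses a new-or-worse condition, and none says that the day-7 check precedes dosing. The grading scale does not fill the gap, because it grades by treatment change and not by change in the measurement.

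**Inputs for an illustration**
- Pilot glucosuria (Appendix 1.2): 6/12 = 0.500 on prednisone, 1/12 = 0.083 on placebo. These are treated here as new-event rates, which is an assumption: the protocol does not say how the pilot handled glucosuria present at entry.
- n = 42 per arm (Section F).
- q = share of participants already above the cut-off before dosing, equal in both arms and all counted. The documents do not give q, so a range is shown.

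**Plan's own figure.** The sample size is for the primary outcome and is reproduced only to confirm the power formula. With a pooled variance under the null, two-sided 5% and no continuity correction:

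z = [d√n − 1.96√(2p̄(1−p̄))] / √(p₁(1−p₁) + p₂(1−p₂))

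For 30% v 60% at n = 42: z = (0.3×6.481 − 1.96×0.7036)/0.6708 = 0.843, so power is 80.0%. This agrees with the stated 42 per arm.

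**Dilution.** Observed rate = q + (1−q)p. The risk difference is therefore multiplied by (1−q), and the risk ratio moves towards 1.

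| q | Placebo | Prednisone | Difference (points) | Ratio | Power, 42/arm |
|---|---|---|---|---|---|
| 0 | 8.3% | 50.0% | 41.7 | 6.0 | 99% |
| 10% | 17.5% | 55.0% | 37.5 | 3.1 | 96% |
| 20% | 26.7% | 60.0% | 33.3 | 2.25 | 88% |
| 30% | 35.8% | 65.0% | 29.2 | 1.8 | 77% |

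Example at q = 10%: 0.10 + 0.90×0.083 = 0.175 and 0.10 + 0.90×0.50 = 0.55; 0.55/0.175 = 3.1.

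**Hypertension.** The pilot had 2/12 in each arm, so there is no contrast to dilute, but the counts still inflate. At q = 10%, each arm shows 0.10 + 0.90×0.167 = 25%, of which 0.10/0.25 = 40% was present before dosing.

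**Hyperglycaemia.** Because serum glucose depends on a dip above 2+, there is no routine day-7 serum value. A day-7 reference exists for the dip and blood pressure, but for serum glucose only where it was drawn. The two stated units also differ: at about 18 mg/dL per mmol/L (assumed), 200 mg/dL is 11.1 mmol/L and 13 mmol/L is 234 mg/dL. They must be reconciled.

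**The case against.** The strongest reply is that little is lost. Allocation is 1:1 and blinded, so pre-existing abnormalities fall equally in expectation. At q = 10% the risk difference moves by about 4 points and power by 3, and an excess as large as the pilot's would still be seen. Blinded investigators judge relatedness, which may set aside some long-standing abnormalities. Section K is a statement of future directions, not a decision rule, and Section G names no test for adverse events. All of this stands and limits the size of the point. It does not remove it, because outcome vi counts events whatever their relatedness, and no rule makes sites treat pre-existing abnormalities alike.

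Several stronger readings are tempting and are not supported:
- A reader might infer that both day-7 checks are taken after dosing. The phrase about being on study drug is attached to urine glucose only. Randomisation follows day-7 spirometry, so a pre-dose check is plausible; it is simply not stated.
- A reader might take 10% from Section F as the insulin-treated share of the trial. That figure stands in the sentence that calls such patients excluded, so it cannot be used as their prevalence here.
- A reader might infer that the percentile gives no value for adults. The documents supply only the table's title, not its age range.
- A reader might say that severity is scored on these cut-offs. They decide only whether an event exists.

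**Conclusion.** The point holds as a gap in the event definitions that is worth correcting. As written, abnormalities present before dosing count as adverse events in both arms, and the contrast in outcome vi is diluted. This is not a systematic imbalance between arms, and it should not be read as making a large excess undetectable. The size depends on q, which is unknown: over an assumed 10% to 30% the glucosuria risk ratio would be 3.1 to 1.8 instead of 6.0, with power of 96% to 77% instead of 99%. These figures also assume that the pilot rates are new-event rates and that every pre-existing case is counted.

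How far diabetes contributes turns on a contradiction: Section F treats insulin use as an exclusion, the Section C list does not, and Section G and Appendix 1.2 plan for diabetic participants. These places must be reconciled. On hypertension the supportable statement is narrower: adults are enrolled, one percentile rule is given, and no separate adult criterion is named.

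**What to change.** - In Table 2 and Appendix 1.2, require the scheduled day-7 urine dip and blood pressure before the first dose of study drug.
- For outcome vi, count glucosuria and hypertension as treatment-emergent only if absent at that check or worse afterwards, with worse defined in advance. Tabulate day-7 abnormalities by arm.
- Report change in systolic and diastolic pressure from day 7 to days 10 and 14 by arm. This needs no age-specific cut-off.
- For hyperglycaemia, use the day-7 dip as the reference, with the serum value where one was drawn, and say that most participants may have no day-7 serum glucose.
- Have the sponsor state which hypertension definition applies to adults, and reconcile the two glucose units and the statements on insulin-treated diabetes.

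The cost is wording in Appendix 1.2, Table 2 and outcome vi, plus two short tables. The dip and blood pressure are already scheduled, so no new measurement is needed. The downside is slightly lower raw event counts in both arms.

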pulmonary function data points were available (n=228), we determined that 50% of patients will recover >90% of their baseline FEV₁ at day 7 of antibiotic treatment, with the remaining 50% available for randomization to either prednisone or placebo treatment. Of the 50% who do not recover >90% of baseline FEV₁ at day 7, 30% of these will go on to recover FEV₁ at day 14 of antibiotic treatment. We therefore estimated a 30% placebo response rate. Using these estimates, we calculated the sample size (**power two proportions** command in Stata 13.1) for the comparison of two proportions (Table 3).

For this study, we are aiming for a clinically significant treatment effect size of approximately two and a half-fold (30% response in the placebo arm vs 60% in the treatment arm). In order to have 80% power (at a significance level of 5%) we would need a sample size of **84 (42/arm)**. Estimating a 50% participation rate and a 20% drop out rate, we will need to approach 210 patients.

Since 50% of all patients who present with a PEx recover their lung function by day 7 of antibiotic therapy, 30% of patients will not experience more than a 10% relative drop in FEV₁ (inclusion criteria) and 10% of CF patients have diabetes and are on insulin which is an exclusion criteria (CPDR 2012 and personal communication-CF clinic directors), we will need to screen approximately 650 exacerbation events to approach 210 patients and enroll 105 patients into the study (Table 3). Over the 3 year study period, we expect to enroll enough study participants from all study sites) which will give us a sufficient population from which to enroll our necessary study sample size. We have had face to face meetings and discussions with our team of co-investigators who have been involved in the design and are fully committed to participating in this study. We have successfully collaborated with this team of researchers in previous clinical trials (10, 51) and fully expect we will achieve our current stated aims.

G. Statistical analyses

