When target sample size is reached, the study statistician (who will not be involved in the conduct of the study) will unblind the treatment allocation (identify who is in group A vs B but not identify the groups themselves as active drug or placebo) and estimate the treatment effect between the two groups based on the primary outcome (intention-to-treat). If there is a statistically significant treatment effect ($p<0.05$), the study statistician will do the following statistical analyses. For the primary outcome we will compare the proportion of randomized patients that responded at day 14 of therapy in the placebo arm compared with the treatment arm using a two sample test for proportions. We will perform intent-to-treat analysis according to the treatment arm subjects were randomized to. We will also perform a per-protocol analysis based on subjects who completed the 7 days of prednisone or placebo as per protocol. The same analysis will be performed for the proportion responding to therapy at 1 month. Logistic regression analysis will then be performed to adjust for potential confounders, such as age, gender, *Pseudomonas aeruginosa* or methicillin-resistant *Staphylococcus aureus* (MRSA) infection and lower FEV₁, as these factors have been associated with failure to recover lung function after an exacerbation (3, 25). For the additional secondary outcomes, absolute change in pulmonary function tests, length of hospitalizations and change in sputum measurements,

we will use parametric (t-test), or non-parametric (Mann-Whitney) two sample comparison test. Linear regression analysis will be then performed to adjust for potential confounders, as listed above. Time to subsequent exacerbation will be compared using a Cox proportional hazard model. Potential confounders will be adjusted for in the Cox-proportional hazard model. All secondary outcomes will be analyzed both as intention-to-treat and per-protocol. All outcomes will be obtained for all subjects irrespective of whether they completed the study per protocol. In the case of missing data, we will perform the analysis on complete (complete case analysis). To determine whether diabetic patients have a different response compared to non-diabetic patients, we will perform a sensitivity analysis comparing return to baseline lung function in diabetics vs non-diabetics according to treatment group.

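### The plan does not separate stopping study drug from leaving the study, so a toxicity stop could cost the day-14 outcome that Section G says is collected for everyone

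*Combined protocol and SAP*

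**What the plan says.** Three statements in the safety text bear on what happens after toxicity:

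- Appendix 1.2, Safety Monitoring Plan, on patients with diabetes: "Diabetic patients for whom glucose control has become unmanageable will be discontinued from the study", on the treating physician's assessment.
- The same section, on patients in general: "The decision to withdraw a subject based on adverse events of hypertension or hyperglycemia will be made by the treating physician".
- Section D, Safety monitoring, repeated in Appendix 1.2, on treating physicians who receive the glucose results: "they can decide at any time to withdraw their patient and request unblinding of the treatment allocation".

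Only the first says what the patient leaves, and it names the study. The other two do not say whether withdrawal is from study drug or from follow-up.

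Section G, Statistical analyses, sets an intention-to-treat primary analysis by randomised arm and states: "All outcomes will be obtained for all subjects irrespective of whether they completed the study per protocol". It then handles missing data by complete-case analysis. Section E, secondary outcome vi, grades hypertension and hyperglycaemia as events that lead to treatment being discontinued. It also counts withdrawals from the study, with reasons.

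**The concern.** Study drug is given from day 7 to day 14, and the primary outcome is FEV₁ recovery at day 14. A toxicity stop during the course therefore comes before the endpoint. Two sites could treat the same event differently. One stops the capsules and measures FEV₁ on day 14. The other takes the patient out of the study and records nothing further. In the second case the complete-case rule drops the patient from a comparison labelled intention-to-treat.

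The triggers are known prednisone effects, so such losses would probably fall more on the active arm. That arm would then be represented partly by those who tolerated the drug. Adverse-event and one-year exacerbation follow-up would be lost in the patients most informative for safety. The planned comparison of diabetic and non-diabetic patients by arm would be thinned. The observed rates used for the sample-size recalculation in Section G and Appendix 1.1 could also be distorted.

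**Working it through.** **1. The plan's own figure.** Section F assumes "30% response in the placebo arm vs 60% in the treatment arm", with 80% power at the 5% level. Allocation is 1:1 (Section D). The test is taken as two-sided, which is not stated but reproduces the result. With a mean rate of 0.45:

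n per arm = [1.96·√(2·0.45·0.55) + 0.842·√(0.3·0.7 + 0.6·0.4)]² / 0.30² = (1.379 + 0.565)² / 0.09 ≈ 42.

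This matches the stated 42 per arm, 84 in total. Section F continues: "Estimating a 50% participation rate and a 20% drop out rate, we will need to approach 210 patients". Here 84/0.8 = 105 and 105/0.5 = 210. The sample-size arithmetic is sound, and the 20% is not split by arm or cause.

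**2. How many could be affected.** The documents give two partial guides.

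- Pilot trial (Section B.2 and Appendix 1.2): 2 of 12 prednisone patients stopped, one for hypertension and one for hyperglycaemia. 2/12 = 16.7% (exact 95% CI 2.1% to 48.4%), and 0.167 × 42 = 7 patients.
- Section F: 10% of patients have insulin-treated diabetes. 0.10 × 42 ≈ 4 patients, if every one of them were lost.

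**3. Effect on the observed prednisone rate.** Let w be the share of the prednisone arm without a day-14 value, q the recovery rate among those lost, and p the true rate in the arm. The complete-case rate is (p − w·q)/(1 − w). Loss is assumed in the prednisone arm only. With p = 60%:

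| Lost | q = 0% | q = 30% | q = 60% | q = 100% |
|---|---|---|---|---|
| 7 of 42 | 72% | 66% | 60% | 52% |
| 4 of 42 | 66% | 63% | 60% | 56% |

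For example, with 7 lost and q = 0 the rate is 0.60/(35/42) = 72%. With q = 100% it is (0.60 − 0.167)/0.833 = 52%. The extremes are +12 and −8 points for 7 lost, and about +6 and −4 points for 4 lost. The shift is zero when those lost recover like the rest of the arm.

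**4. Effect on the test** (normal approximation, 42 placebo patients).

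- Power at unchanged rates: 80.0% with nobody lost, 78.0% with 4 lost, 76.2% with 7 lost.
- Rejection rate when both true rates are 30% and 7 are lost: 5.0% if q = 30%, 6.0% if q = 15%, 8.7% if q = 0.

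If 105 are enrolled (about 52 per arm) and 9 are lost from prednisone, power is 84.5%. The dropout allowance therefore covers the loss of numbers, but it does not cover selective loss.

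**The case against.** A reader might infer that the safety rules flatly contradict Section G and that prednisone patients will be selectively removed from the primary analysis. The documents do not support that, for four reasons.

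- **Section G can be read as already covering these patients.** It promises outcomes on non-completers and defines a separate per-protocol set, so the plan expects people who stop drug to stay in the main analysis. Appendix 1.2 never says that data collection ends.
- **Withdrawal is used loosely.** Section B.2 says that two pilot patients discontinued prednisone, and Appendix 1.2 describes the same two as withdrawn. Both Section E and the Appendix 1.2 grading scale speak of treatment being discontinued. For hypertension and for hyperglycaemia in general, withdrawal is at the physician's discretion and may mean drug only.
- **Day-14 spirometry is standard clinical care** (Section D and Table 2), so the value may exist even after a patient leaves the study.
- **The size is soft.** The 2 of 12 counts stops for any toxicity under a 5-day course, and nothing says that those patients' outcomes were lost. The placebo arm's stops are not reported. Against an assumed 0 of 12, Fisher's p is 0.48. Section F calls insulin-treated diabetes an exclusion, whereas the Section C list omits it and Appendix 1.2 plans for such patients on study drug. The number affected is therefore unclear.

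All of this stands, and it limits the point to a possible loss of unknown direction. It does not remove the point. The diabetic sentence names the study as what the patient leaves, nothing says that the day-14 value is still collected and used afterwards, and Section F's 20% dropout shows that the plan itself expects some losses.

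**Conclusion.** The point holds as an unreconciled conflict with a possible effect on the primary analysis. It is firm for the diabetic sentence and a matter of ambiguity for the general withdrawal wording. Bias needs three things together: a site reads the text as ending participation, the day-14 FEV₁ is then missing or unused, and those lost differ in recovery from the rest of their arm.

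Under the assumptions above, the prednisone rate moves by at most +12 to −8 points at the pilot's stop rate, and by at most about +6 to −4 points if only the insulin-treated are lost, against a 30-point target difference. Both ranges take extreme cases, in which all those lost failed or all recovered. More loss on prednisone is likely from the pharmacology the plan describes (glucosuria in 6 prednisone patients and 1 placebo patient in the pilot), but the documents do not establish it. The plan should be changed before the primary analysis because the remedy is cheap and removes this source of selection.

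**What to change.** Reconcile the safety text in Section D and Appendix 1.2 with Section G:

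1. Define discontinuation of study drug and withdrawal of consent to follow-up as two separate events, and use the terms consistently.
2. State that after a drug stop or unblinding, scheduled outcomes are still collected unless consent is withdrawn: day-14 and 1-month FEV₁, adverse events, and one-year exacerbation follow-up. State that they are analysed in the randomised arm.
3. Record the two events separately, with reasons and by arm, under secondary outcome vi.
4. Reconcile the statements on insulin-treated diabetes in Sections C and F and Appendix 1.2, so that the size of the affected group is known.

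The decision on whether and when to stop study drug stays as the protocol has it. The cost is protocol wording, one form field, and continued follow-up of a few patients whose FEV₁ visits are already standard care. Patients who withdraw consent will still be missing, and the complete-case rule will still apply to them.
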